The PI will have ultimate responsibility for event reporting. Monitoring will occur by the research team, who will then bring all AEs to the attention of the PI. Co-Is [name] or [name] will be consulted for evaluation and gradation of AEs. The PI and the study manager/coordinator will be responsible for overseeing data integrity, safety monitoring, and reporting of adverse events.

Training in Fair, Responsible, and Ethical Conduct of Research

The PI and the research team have undergone training in fair and ethical conduct of research in general and on human participants. The PI and the research team have taken HIPAA training mandated by WSU. An additional consent form consistent with the HIPAA 2003 rules will be used to educate the research participants and obtain informed consent regarding safeguards for the privacy and security of health information.

6. ClinicalTrials.gov Requirements

This project includes an applicable clinical trial, which will require registration in ClinicalTrials.gov. The responsible party is the principal investigator of this project: [name].

Bibliography and References Cited

- 1 Kessler, R. C. *et al.* Lifetime prevalence and age-of-onset distributions of DSM-IV disorders in the National Comorbidity Survey Replication. *Arch Gen Psychiatry* **62**, 593-602, doi:10.1001/archpsyc.62.6.593 (2005).
- 2 Kessler, R. C. *et al.* Lifetime and 12-month prevalence of DSM-III-R psychiatric disorders in the United States. Results from the National Comorbidity Survey. *Arch Gen Psychiatry* **51**, 8-19 (1994).
- 3 APA. *Diagnostic and statistical manual of mental disorders IV-TR*. 4th, text rev. edn, (Amer Psychiatric Pub Inc., 2000).
- 5 Hoge, E. A., Austin, E. D. & Pollack, M. H. Resilience: research evidence and conceptual considerations for posttraumatic stress disorder. *Depress Anxiety* **24**, 139-152, doi:10.1002/da.20175 (2007).

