Specific Aim 1 (R61 Primary Target Engagement): Assess effects of THC on recall of extinction learning and vmPFC and/or HPC activation in PTSD patients in a dose-finding study. *Hypothesis 1A: Relative to PBO, THC will dose-dependently increase vmPFC and/or HPC activation to a CS+E (vs. CS+U) during proximal (24 hr post-extinction learning) and/or distal (1 week post-extinction learning) recall of extinction learning in PTSD.* PCS (CS+E vs. CS+U) with ROIs (vmPFC, HPC) will be submitted to MANCOVA with Group (PTSD-5mg, PTSD-10mg, PTSD-PBO, TEC) as between-subjects factor and Recall (24 hr, 1 week) as within-subject factor, controlling for potential confounds. In addition to omnibus tests, planned comparisons will examine dose of THC on prefrontal-limbic engagement during recall of extinction learning in PTSD relative to PBO, and comparisons between THC doses; if there is no significant difference between THC doses we will examine potential positive trends with increasing dose. Similar analyses will be conducted using other variables of interest such as psychological measures, mood state, and drug effects. *Hypothesis 1B: Relative to PBO, THC will dose-dependently decrease peripheral measures of extinction recall (“extinction recall index” (ETI), US expectancy, SUDS) to the CS+E during a proximal and/or a distal test of extinction learning recall in PTSD.* These data will be submitted to MANCOVA with Group (PTSD-5mg, PTSD-10mg, PTSD-PBO, TEC) as between-subjects factor and Recall (24 hr, 1 week) as within-subject factor, controlling for potential confounds. Analyses will be comparable to that used to examine BOLD activation (*Hypothesis 1A*). *Hypothesis 1C: vmPFC and/or HPC activation will correspond with extinction recall success (i.e. higher ETI, lower US expectancy, lower SUDS).* Pearson correlation analyses will be used to correlate measures of BOLD activation (PSC) and peripheral measures (e.g., SCR, ETI, US expectancy) to the CS+E vs. CS+U within and across the two contexts/recall and renewal tests.

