DEQ**			✓	✓	✓	

ARCI**			✓	
ESQ**			✓	
Blood Draw Safety Questionnaire**			✓	
Debriefing Interview				✓

***These measures are NOT completed by the TEC group at Visit 3, as they do not ingest THC/PBO*

Secondary Measures (Table 1)

(1) Standard Health Questionnaire; (2) Ethnicity/Racial Category Form; (3) MRI Safety Form; (4) Gender Identity

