
Additional Secondary Measures (Table 1)

In addition to standardized assessments of symptom severity and mood/emotional state, the following measures will be completed at various time points within a session (e.g., before, during, and after) on days in which fear acquisition and/or fear extinction and extinction recall/fear renewal tests occurs: (1) US expectancy; (2) Subjective Units of Distress Scale (0=absolutely calm; 100=worst distress), frequently used in exposure-based therapy, which will provide a measure of subjective fear.

THC/PBO Day Measures (Table 1)

The following standardized assessments will be collected throughout the session when THC/PBO is ingested to assess mood states and subjective drug effects. These questionnaires are sensitive to the effects of a variety of psychoactive drugs on affective state/mood and drug liking^{172,173}: (1) Visual Analog Scales (VAS): This questionnaire consists of visual analog scales used to describe current medication effects. This particular form consists of twenty 100-mm horizontal lines each labeled with an adjective ("clear-headed," "anxious," "stimulated," "tired," "calm," "drowsy," "peaceful," "nervous," "hungry," "energetic," "uneasy," "relaxed," "alert," "content," "focused," "dreamy," "restless," "nauseous" "worn out," and "jittery"). The left end of each line is labeled "not at all" and the right "extremely." Participants are instructed to place a mark on each line indicating how they feel at the moment; (2) Drug Effects Questionnaire (DEQ)¹⁷⁴: This questionnaire assesses the extent to which participants "feel any substance effect(s)," "feel high," "like the effects," "dislike the effects," and "want more of the substance" using 100 mm visual analog scales. The left end of each line is labeled "not at all" and the right "extremely." Participants are instructed to place a mark on each line indicating how they feel at that moment; (3) Addiction Research Center Inventory (ARCI)^{175,176}: The 53-item ARCI is a true-false questionnaire with five

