empirically derived scales that are sensitive to the effects of a variety of classes of abused drugs. The scales are the MBG (Morphine-Benzedrine Group), a general measure of drug-induced euphoria; the A (Amphetamine) scale, a measure specific for dose-related effects of d-amphetamine; the BG (Benzedrine Group), an amphetamine scale consisting mainly of items relating to intellectual efficiency and energy; the PCAG (Pentobarbital-Chlorpromazine Group), a measure of sedation; the LSD (Lysergic Acid), a measure of dysphoria and somatic symptoms; and the M scale, a measure of marijuana's effects; (4) Spielberger State-Trait Anxiety Inventory (STAI)¹³¹ (state subscale): This state subscale is used to assess the level of state (current/in the moment) anxiety in an individual; (5) At completion of drug session, participants will complete the End of Session Questionnaire (ESQ) which asks them to indicate the extent to which they think they felt a drug effect, the extent to which they think they received THC or PBO, and to rate how much they "liked its effects." They will be also asked to comment on any unusual effects they experienced, and whether they would take the substance again. In addition, physiologic measures (heart rate, blood pressure) will be collected at regular intervals throughout the drug session. (6) The Blood Draw Safety Questionnaire will be completed by the participant at the beginning of the THC/PBO session (Visit 3) and reviewed prior to blood collection at all subsequent visits.

These psychological and physiological measures are collected 1) before receiving THC or PBO on Visit 3; 2) at approximately 30 min intervals after receiving THC or PBO on Visit 3 (i.e., at 30, 60, & 90 min), immediately before going in the MRI scanner, soon after coming out of the MRI scanner; and once before the end of the visit unless otherwise specified (ESQ will be collected only at the end of the drug session; DEQ will also be collected before recall of extinction learning on Visits 4 & 5). Because the effects of the drugs may have a lingering effect, measures of the effects of the drug (DEQ) and review of adverse events will also be collected for exploratory purposes at two additional times: approximately 8 hr after drug administration.

Debriefing Session Measures

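### The model extended to mood and drug-effect measures does not match when and in whom most of them are taken, and no stated model uses their pre-capsule value

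*Combined protocol and SAP*

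**What the plan says.** The model in C.2.9, Hypothesis 1A has "Group (PTSD-5mg, PTSD-10mg, PTSD-PBO, TEC) as between-subjects factor" and "Recall (24 hr, 1 week) as within-subject factor, controlling for potential confounds". After the planned contrasts (dose v PBO, dose v dose, dose trend) it adds: "Similar analyses will be conducted using other variables of interest such as psychological measures, mood state, and drug effects".

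The schedule for these measures is under Protection of Human Participants, Sources of Materials. The THC/PBO Day Measures (VAS, DEQ, ARCI, state STAI, ESQ) "will be collected throughout the session when THC/PBO is ingested to assess mood states and subjective drug effects". On timing: "These psychological and physiological measures are collected 1) before receiving THC or PBO on Visit 3", then "at approximately 30 min intervals after receiving THC or PBO on Visit 3 (i.e., at 30, 60, & 90 min"), then before the scanner, after the scanner and at the end of the visit. ESQ is taken only at the end of the session. "DEQ will also be collected before recall of extinction learning on Visits 4 & 5", and a further DEQ reading about 8 hr after dosing is called exploratory. The footnote to the starred rows of Table 1 reads: "These measures are NOT completed by the TEC group at Visit 3, as they do not ingest THC/PBO".

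C.2.5 names ANOVA for psychological and mood measures. It gives no groups, time points or baseline term for them, and admits covariates only if they are unbalanced and correlated with the outcome. C.2 has a second rule: variables that differ between groups at p<0.05 become covariates in the primary analyses.

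**The concern.** The word similar has one model to point to, and most of the scales named for this purpose are not measured at that model's visits or in its fourth group. The analyst must then choose, per scale, which arms, which of the six post-capsule times and which treatment of the pre-capsule reading to use. Those choices would be made with the data in hand. C.2.2 says such measures are meant to show change over time in mood and anxiety, yet no stated model contains time within Visit 3 or the starting value. What is at stake is the precision and pre-specification of the subjective-effect comparison between 5mg, 10mg and PBO, which is secondary information in a dose-finding study.

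**Working it through.** The plan gives no figure on this point, so there is none to reproduce. The check has two parts.

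**1. Does the layout have data?** Four groups x two recall visits give 8 cells: 3 PTSD arms x 2 = 6, and TEC x 2 = 2. From Table 1, its footnote and the THC/PBO Day Measures text:

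| Measure | PTSD cells (of 6) | TEC cells (of 2) | Filled (of 8) |
|---|---|---|---|
| VAS | 0 | 0 | 0 |
| ARCI | 0 | 0 | 0 |
| ESQ | 0 | 0 | 0 |
| State STAI, post-capsule | 0 | 0 | 0 |
| DEQ | 6 | not stated | 6 |
| SUDS (for comparison) | 6 | 2 | 8 |

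The drug-session heart rate and blood pressure readings follow the Visit 3 schedule too. The general safety procedures also mention monitoring both during fMRI sessions, so readings at Visits 4 and 5 may exist.

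Visit 3 time points: 1 before the capsule + 3 (30, 60, 90 min) + 1 before the scanner + 1 after it + 1 at the end of the visit = 7, of which 6 are post-capsule.

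**2. What would the pre-capsule value add?** Set the variance of a post-capsule score to 1, assume equal variance before and after, and let rho be the correlation between the pre-capsule value and a given post-capsule value. The documents give no rho, so a range is assumed. The variance of the arm comparison is then proportional to:

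- post-capsule score alone: 1
- change from pre-capsule: 2(1 - rho)
- adjusted for pre-capsule: 1 - rho^2

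| rho (assumed) | Post only | Change | Adjusted | Reduction v post only |
|---|---|---|---|---|
| 0.3 | 1 | 1.40 | 0.91 | 9% |
| 0.5 | 1 | 1.00 | 0.75 | 25% |
| 0.7 | 1 | 0.60 | 0.51 | 49% |

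Adjustment has the smallest variance in every row. Against a change score the saving is 1 - (1 + rho)/2 = (1 - rho)/2, that is 35%, 25% and 15%.

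With the expected 20 completers per arm, two-sided 0.05 and no multiplicity adjustment, the difference detectable with 80% power is sqrt(2v/20) x (1.96 + 0.84), where v is the variance above. This is 0.886 SD for a post-capsule score alone. With adjustment it is 0.845, 0.767 and 0.633 SD at rho 0.3, 0.5 and 0.7.

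**The case against.** The best defence is that the text says similar, not identical. The planned comparisons just before that sentence (dose v PBO, dose v dose, trend) need neither TEC nor the Recall factor and can be run on Visit 3 data, and C.2.5 separately names ANOVA for mood measures. This stands. A reader might infer that these analyses cannot be run at all; the documents do not support that. The plan leaves the model open rather than making it impossible.

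Nor are all the measures confined to PTSD participants at Visit 3. SUDS is scheduled at both recall tests for every group, DEQ is also taken later, and STAI is also marked at screening with no TEC exemption there.

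A reader might also infer that the tolerability side of dose finding is left without an analysis. It is not. The Data and Safety Monitoring Plan provides formal comparisons of adverse-event frequency, and its dose-review criteria use none of VAS, DEQ, ARCI or STAI.

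A third tempting inference is a definite power gain. For 20 v 20 and a 0.72 SD difference, a t-based calculation gives 60.2% without adjustment and 64.2%, 72.6% and 87.4% at rho 0.3, 0.5 and 0.7. But rho is assumed, and 0.72 SD comes from a power statement about fMRI effects, not mood or drug-effect scales. The plan also never commits to a post-only score: a repeated-measures ANOVA with the pre-capsule time as a level would use that value. DEQ items on feeling a drug effect or a high may sit near floor before dosing, where adjustment adds little.

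What survives is that no stated model names the pre-capsule value or the Visit 3 time course, and the two conditional covariate rules do not fill the gap.

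**Conclusion.** The point holds as an improvement to secondary analyses that costs no data. The Group x Recall model has no data for VAS, ARCI, ESQ and post-capsule state STAI. It covers DEQ only in the PTSD arms, from about a day after the single dose onwards. Unwritten model detail alone would be a minor matter. The stronger reason to act is that unconditional adjustment for a value already collected is a better method than ANOVA with covariates added only on imbalance and correlation. At each assumed correlation it beats both a post-only and a change score. Its size is a 9% to 49% cut in residual variance relative to post-only for rho 0.3 to 0.7, given equal variances and a roughly linear pre/post relation, and less for items near floor. The BOLD, ETI, US expectancy and SUDS outcomes of Hypotheses 1A to 1C and the adverse-event comparisons do not change.

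**What to change.** Replace the sentence in C.2.9 with explicit wording:

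- For VAS, DEQ, ARCI, state STAI and the drug-session heart rate and blood pressure: the three PTSD arms only, in a mixed model with Arm, Time (six post-capsule Visit 3 points) and Arm x Time. The pre-capsule value enters as a covariate in every case, outside the conditional rules of C.2 and C.2.5. Estimate each dose v PBO with a confidence interval, and say whether the main contrast is the average over the six points or is at named points.
- For ESQ: a single between-arm comparison, as it has no pre-capsule value.
- For the DEQ reading at about 8 hr and those at Visits 4 and 5: a separate analysis of residual effect in the PTSD arms. The text announces two extra times but lists only one, so the schedule should be reconciled.
- Keep the four-group Group x Recall model for measures that fill it, such as SUDS.

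The cost is SAP wording, settled before unblinding, and modest programming. No extra data, visits or participants are needed.

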extinction recall test, but no more than 3 weeks later (Extinction Recall Visit 5), in which participants will be presented with the CS+E, CS+U, and CS- (no snake) in Context B. Contrasting CS+E and CS+U during extinction recall in Context B will allow us to assess physiological and brain responses specific to recall of extinction learning and independent from recall of fear acquisition. To test for contextual renewal of fear (context shift from the extinction context [B] to the conditioning context [A]), we will conduct a proximal fear renewal test approximately 24 hr after extinction learning, but no more than 1 week later (Fear Renewal Visit 4) and a distal fear renewal test approximately 1 week later, but no more than 3 weeks later (Fear Renewal Visit 5), in which participants will be presented with the CS+E, CS+U, and CS- (no snake) in Context A. Stimulus parameters will be similar to those conducted in our previous studies¹¹³. During all sessions, our primary measures of conditioned fear will be SCR magnitude and US expectancy ratings for each CS trial. Extinction Learning (Visit 3) and Extinction Recall/Fear Renewal Visits 4 & 5 will be conducted in the MRI scanner with simultaneous recording of SCR and US expectancy ratings, except in the event a participant is unable to be scanned, in which case these visits will be conducted outside the scanner in the PI's research laboratory. Fear acquisition (Visit 2) will be conducted outside of the scanner in the PI's research laboratory. During all sessions, our primary measures of conditioned fear will be SCR magnitude and US expectancy ratings for each CS trial¹²⁹.

Genotyping: DNA extraction and genotyping of the rs324420 variant will be completed in [name] laboratory (see letter). If the participants signs the DNA consent form, DNA will be extracted from buccal swabs using Quiagen buccal DNA kits.

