C.2.4. fMRI: MR scanning at WSU will be performed on a 3.0 Tesla Siemens Magnetom Verio System using an industry-leading 32-channel head-coil for superior image quality. We will use a multi-band EPI sequence [similar to: TR = 2000ms; TE = 30ms; Flip = 73°; 128x128 matrix; FOV = 256 mm; 66 slices; 2.0 x 2.0 x 2.0 mm voxels], which we are currently using in PI [name]'s K01 project. A high-resolution structural image will provide precise anatomical localization. Whole-brain fMRI blood oxygen-level dependent (BOLD)-related signal measures will be acquired to measure task- and drug-related effects and to minimize susceptibility artifact (signal loss) at the medial temporal lobe (including the AMYG and the vmPFC)¹³³⁻¹³⁵.

C.2.5. General Statistical Approach: All analyses will use a conventional alpha level of 0.05 and all tests will be two-tailed. To evaluate the main effects, Analysis of Variance will be used for neuroimaging (i.e., BOLD percent signal change (PSC)) and peripheral measures of fear (e.g., SCR, US expectancy, SUDS, psychological/mood measures). We will also include covariates such as gender and childhood trauma/adversity

if found unbalanced and correlated ($r > 0.03$) with the outcome variable (e.g., MANCOVA, ANCOVA). If significant, multivariate analysis will be followed by univariate analysis, which if significant, will be followed-up with simple effects analysis (e.g., independent t-tests, paired t-tests). In addition to omnibus tests, planned comparisons will be used to test specific hypotheses such as THC dose (vs. PBO) on fear extinction in PTSD, as well as comparisons between THC doses; if there is no significant difference between THC doses we will examine potential positive trends with increasing dose. To evaluate relationships, Pearson correlations will be used along with scatterplots to examine the nature of the relationships. Hochberg step-down multiplicity adjustment will be used to control for all multiple comparisons¹³⁶. Confidence intervals and effect sizes will be also be calculated.

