R61 Power Analysis: We have conducted several power calculations in our previously published work used to determine the sample sizes proposed here. First, we have consistently found that an *n* of 14-16 healthy controls and an *n* of 14-16 PTSD patients provide adequate power to observe: 1) SCR differences and AMYG, vmPFC, HPC signal differences between groups during fear extinction and/or extinction recall; and 2) THC's effects on ETI and AMYG, vmPFC, and HPC activation in healthy controls. Similarly, normalization of corticolimbic responsivity to affective stimuli has been observed following exposure-based therapy in an *n* of 14 anxious patients¹⁴⁸ and following administration of a serotonin selective reuptake inhibitor (SSRI) with an *n* of 21 anxious patients¹⁴⁹. Given that the effect sizes tested within- and between-groups in previous fMRI studies have ranged between moderate to large (Cohen *d* = 0.7 - 1.5) with the anticipated cohort of 20 participants per group (PTSD-5mg, PTSD-10mg, PTSD-PBO, TEC), who complete the entire protocol with usable fMRI and SCR data, will confer >80% power to detect an effect size 0.72 or higher after necessary multiplicity adjustment.

PROTECTION OF HUMAN PARTICIPANTS

This Human Participants Research meets the definition of a clinical trial.

1. Risks to Human Participants

a. Human Participants Involvement, Characteristics, and Design

Involvement of Human Participants:

The total time commitment estimated per participant is 8.5-13 hr across all study visits. This is broken down below:

Visit 1: Screening & Study Entry: Approximately 3 hours for participants, unless a participant has already completed any of the screening assessments as part of another separate study. In this case, if the overlapping screening assessments were completed no more than 1 month prior to Visit 1 and the participant has signed HIPPA Authorization allowing us to access this prior data, Visit 1 will be approximately 1.5 hr.

Note: Due to the length and rigor of this initial screening process, it may sometimes be necessary for participants to complete screening measures across more than one visit (e.g., schedule conflicts). All screening measures will be completed within 2 weeks of the consent date.

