
Termination Criteria

Participants may be terminated for any of the following: (a) participant request to exit or withdraw consent; (b) development of risk of harm to self or others that requires immediate intervention; (c) alcohol, drug, medication use that would interfere with dronabinol or has level 1 evidence for severe drug-drug interaction with dronabinol; (d) development of a systemic, medical, neurologic, or psychiatric illness requiring treatment that would exclude participation; (e) clinical deterioration (see below); (f) non-compliance with study protocol requirements. We will make every effort to ensure that the sessions are accessible (i.e., scheduling sessions during evening and weekend hours). We will attempt to schedule Visits 2-4 on consecutive days, but in the event that this is not possible we will allow no more than 1 week between Visits 2 & 3 and Visits 3 & 4 and no more than 3 weeks between Visits 4 & 5. Of note, if there is more than 1 week between Visit 2 & 3, we will re-do Visit 2 and proceed with the rest of the visits as normal. But once a participant completes Visit 3, Visits 4 & 5 need to be completed within the above timeframe otherwise participation will be terminated. We will make every effort to ensure that appointments are accessible (i.e., scheduling an appointment during evening and weekend hours).

Medical and Neurological Health Determination

All health information collected in the pre-screening and baseline interview (Visit 1) will be reviewed by the PI or Co-I [name], who will indicate whether the participant is medically and neurologically healthy enough to continue in the study. These determinations may be made in person, over the phone, or via e-mail, and will be documented using a Medical Review form.

Emergent Suicidal or Homicidal Risk

The clinician or research staff may remove a participant from the clinical trial if the PI thinks that the participant is at imminent suicidal or homicidal risk. The presence of suicidal ideation is evaluated at the initial assessment. Endorsement of suicidal or homicidal ideation will be addressed in session. If the patient is deemed to have specific suicidal or homicidal ideation, the PI, Co-I [name], or Co-I [name] will be immediately notified and the participant will meet with the PI and/or Co-Is [name] and/or [name], or other licensed social worker/psychologist/psychiatrist covering for the PI or Co-Is on the premises, and the police will be alerted.

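### Hypotheses 1A and 1B rest on a repeated-measures MANCOVA that, run in the standard way, drops anyone missing one recall visit or one outcome in that model; a mixed model per outcome would keep them

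*Combined protocol and SAP*

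**What the plan says.** Section C.2.9 (Specific Aim 1) names the model for both hypotheses: a MANCOVA with four groups (5 mg, 10 mg, placebo, TEC) and "Recall (24 hr, 1 week) as within-subject factor". Hypothesis 1A puts BOLD signal change in vmPFC and HPC into it. Hypothesis 1B puts in ETI, US expectancy and SUDS. Each hypothesis is worded so that an effect at the 24 hr test, the 1-week test or both would count.

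The protocol foresees incomplete data in several places:
- Protection of Human Participants expects 25% not to finish every part, leaving 20 of 26 per group.
- Termination Criteria: once Visit 3 is done, "Visits 4 & 5 need to be completed within the above timeframe otherwise participation will be terminated".
- Section C.2.1: recall visits take place in the scanner "except in the event a participant is unable to be scanned"; in that case the visit still goes ahead in the laboratory.
- The Psychophysiological and FMRI Data paragraphs make SCR and fMRI collection conditional on being able to obtain them.

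The R61 Power Analysis sizes the study on 20 per group "who complete the entire protocol with usable fMRI and SCR data". No section names an analysis set, a missing-data method or a mixed model. The only stated provision for dropout is enrolling up to 175.

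**The concern.** A standard repeated-measures MANCOVA needs a complete row per person: every outcome in the model at both recall visits. One empty cell removes the person. Three kinds of usable data are then at risk:

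- **Visit 4 without Visit 5.** A participant with a valid 24 hr outcome who misses the Visit 5 window leaves both 1A and 1B, even though the 24 hr effect alone could support either.
- **Ratings without SCR.** In 1B, no usable SCR means no ETI, and the same person's US expectancy and SUDS go too. Section C.2.7 has ETI adjust for conditioned responding at acquisition, so an SCR failure at Visit 2 can do this as well as one at Visit 4 or 5.
- **One scan of two.** In 1A, a usable Visit 4 scan is lost if the Visit 5 scan fails.

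In the PTSD arms these people were randomised and dosed, and the arms are small. Dropping them costs precision. It also relies on completers being representative within arm, a stronger condition than the missing-at-random assumption of a likelihood-based mixed model.

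**Working it through.** **Inputs from the documents.** 26 per PTSD arm; 25% not completing everything; 20 per group for sizing; d = 0.72; "All analyses will use a conventional alpha level of 0.05 and all tests will be two-tailed"; "Hochberg step-down multiplicity adjustment will be used to control for all multiple comparisons". The size of the Hochberg family is not given.

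**The plan's own figures first.**
- Completers: 26 × 0.75 = 19.5, so 20 per group reproduces.
- Power: the plan says 20 per group "will confer >80% power to detect an effect size 0.72 or higher after necessary multiplicity adjustment". For a two-sided between-group contrast at one visit, alpha 0.05, normal approximation: z = 0.72 × √(20/2) − 1.96 = 2.277 − 1.960 = 0.317, giving power 0.624 (0.602 by the t distribution). At alpha 0.025 it is 0.514 (0.484). The stated figure therefore does not reproduce for this contrast. That is a separate issue; 0.624 serves below only as the complete-case baseline.

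**Who enters which model.**

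| Participant | 1A MANCOVA | 1B MANCOVA | Mixed model per outcome |
|---|---|---|---|
| Visit 4 only, all outcomes usable | out | out | in, at Visit 4 |
| Both visits, never scanned, SCR and ratings usable | out | in | in for 1B outcomes; no BOLD to analyse |
| Both visits, scanned, SCR unusable | in | out | in for BOLD, US expectancy, SUDS |
| Lost before Visit 4 | out | out | out |

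**Size of the gain.** Assumptions, not in the documents: n = 20 completers per arm; m = 2 or 4 of the 26 − 20 = 6 others have Visit 4 only; between-visit correlation ρ = 0.5 or 0.7; unit variance; covariance treated as known; missing at random. Per-arm variances of the estimated means:
- Visit 4: V4 = 1/(n + m), against 1/n for completers.
- Visit 5: V5 = (1/n) × [1 − ρ²m/(n + m)], against 1/n.
- Covariance: C = ρ/(n + m).
- Two-visit mean: (V4 + V5 + 2C)/4, against (1 + ρ)/(2n).

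Worked case, m = 4, ρ = 0.5: V4 = 1/24 = 0.04167; V5 = 0.05 × (1 − 0.25 × 4/24) = 0.04792; 2C = 2 × 0.5/24 = 0.04167. The sum is 0.13125; divided by 4 it is 0.03281, against 1.5/40 = 0.03750. Ratio 0.875, √0.875 = 0.935, so the standard error falls 6.5%.

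| m | ρ | SE fall, Visit 4 | SE fall, Visit 5 | SE fall, two-visit mean |
|---|---|---|---|---|
| 2 | 0.5 | 1 − √(20/22) = 4.7% | 1.1% | 3.5% |
| 2 | 0.7 | 4.7% | 2.3% | 3.9% |
| 4 | 0.5 | 1 − √(20/24) = 8.7% | 2.1% | 6.5% |
| 4 | 0.7 | 8.7% | 4.2% | 7.4% |

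At m = 0 every entry is zero. At m = 6, the ceiling, the Visit 4 fall is 1 − √(20/26) = 12.3%.

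**In power terms** (d = 0.72 at each visit, two-sided 0.05, no multiplicity adjustment, normal approximation, m = 2 to 4):
- Visit 4: 0.624 rises to 0.666–0.703.
- Visit 5: 0.624 rises to 0.634–0.661 across ρ = 0.5 to 0.7.
- Two-visit mean: 0.748 rises to 0.777–0.803 at ρ = 0.5, and 0.695 to 0.729–0.760 at ρ = 0.7.

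For US expectancy and SUDS, a person lost only through missing ETI is regained at both visits. With k such people per arm the standard error is multiplied by √(20/(20 + k)) at each visit. The documents give no basis for k.

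**The case against.** The strongest reply is that the plan never says it will delete incomplete cases. That is correct: deletion is inferred from the named method. Termination for a missed window ends participation and says nothing about data already collected. Other planned analyses do not need both visits: the group by stimulus MANCOVA in C.2.6 has no Recall factor, and C.2.5 lists univariate and simple-effects follow-ups. A Visit-4-only participant could enter those. But C.2.5 makes that follow-up sequence conditional on a significant multivariate result. It adds planned comparisons without saying who is in them, and the model named for 1A and 1B in C.2.9 still carries Recall as a factor.

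A reader might infer from the power section that the MANCOVAs demand both usable fMRI and usable SCR. The documents do not support this. That phrase describes the cohort used for sizing, not an analysis set; 1A contains no SCR and 1B no fMRI. Only the correlations in 1C need both kinds of data, and a mixed model would not change that.

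It is also fair to say that the gain is modest and rests on assumed counts. The 25% includes people lost before Visit 4, who add nothing to any recall model. The BOLD signal of someone never scanned cannot be recovered.

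**Conclusion.** The point holds as a cheap improvement. For both hypotheses the plan names a model that, in its standard form, needs complete data on every outcome in that model at both visits. The protocol expects gaps, and no missing-data handling is stated.

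Under the assumptions above, a mixed model lowers the standard error by about 5 to 9% at Visit 4 and 3.5 to 7.4% for the two-visit mean. It gives 1 to 4% at Visit 5, and nothing if nobody has Visit 4 only. It is valid under missing at random, a weaker condition than complete-case analysis needs.

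Two stronger conclusions are tempting and should not be drawn. First, that completers-only results would be materially biased: this depends on a link between response and completion that the documents do not describe, so no size can be given. Second, that the change restores the stated power: even with all 26 per arm at Visit 4, power at d = 0.72 is 0.738 before any multiplicity adjustment.

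**What to change.** In Section C.2.9, make the primary analysis a linear mixed model for each outcome (vmPFC, HPC, ETI, US expectancy, SUDS), with group, visit, group by visit, the planned covariates and an unstructured covariance over the two recall visits.

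State the analysis set for each outcome: every PTSD participant who was randomised and dosed, and every TEC participant, with at least one recall visit for that outcome. TEC must be named separately, because those participants are neither randomised nor dosed. State that missing values are handled by likelihood under missing at random.

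Apply the Hochberg adjustment already planned in C.2.5 across the outcome-specific contrasts, and list the contrasts that form the family. Keep the MANCOVA as a sensitivity analysis.

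The cost is SAP wording and a standard procedure, with no new data. The downside is that the multivariate omnibus test, and the multivariate-then-univariate sequence built on it, are no longer primary.
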